data that illustrate brain activation over time in response to the individual stimulus. *The secondary analysis pathway* includes mathematical models that try to bridge brain function and actual behavior. Computational modeling tries to explain a real world problem in a simplified model that then gets translated into a mathematical equation that can be used to correlate with brain imaging results. This serves the purpose of predicting brain response following a stimulus and depending on factors such as learning rate and received reward, different brain regions will be implicated. That is, the subject performs a specific task or Reward Paradigm and learns under what conditions reward occurs (Figure 3.5). The time course of reward experience is known by the experimenter. In the taste experiment, reward delivery or omission is part of the paradigm and recorded by the stimulus-applying computer.

[figure not shown]

Figure 3.5. Practical application of computational modeling of fMRI data.

Use of mathematical models and testing of alternate models. Taste paradigm: For this paradigm we will use the temporal difference model as described in the past in the original description of this paradigm (O'Doherty et al., 2003). On each trial, the predicted value (V) at any time t within a trial is calculated as a linear product of the weights w_i and the presence or absence of a CS

stimulus at time t , coded in the stimulus representation vector $x_i(t)$:

Learning occurs by updating the predicted value of each time point t in the trial by comparing the value at time $t+1$ to that at time t , leading to a prediction error or $\delta(t)$:

where $r(t)$ = reward at time t . The parameter γ is a discount factor, which determines the extent to which rewards that arrive earlier are more important than rewards that arrive later on. Similar to O'Doherty's study (O'Doherty et al., 2003), we will set $\gamma=0.99$. The weights w_i will be then updated on a trial-by-trial basis

$$\Delta w_i = \alpha \sum_t x_i(t) \delta(t)$$

according to the correlation between prediction error and the stimulus representation:

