where α = learning rate. We will assign six time points to each trial and use each subject's individual event history as input. On each trial, the CS (visual fractal) will be taken to be delivered at time point 1, and the UCS reward (sweet taste stimulus) will be delivered at time point 3. We will, as in O'Doherty (O'Doherty et al., 2003), use as learning rate of the model (α) two values for α : a lower learning rate ($\alpha=0.2$) and a higher learning rate ($\alpha=0.7$). In the original study the lower learning rate modeled best brain activation in the ventral striatum and orbitofrontal cortex. The temporal difference error $\delta(t)$ will be created for the CS and the positive and negative UCS for each time-point and an ideal activation curve will be created and convolved with the hemodynamic response curve. That curve will then be modeled to the functional magnetic resonance imaging data in order to generate brain regions that respond according to the model. Time activity curves will then be created in order to compare actual with predicted brain response over time. We cannot predict whether anorexia nervosa women will have simply reduced brain response to the stimuli or if a different learning rate will apply and explain altered learning response. This will be an empirical task during data analysis.

Reversal Learning Paradigm. We adapted a probabilistic reversal paradigm from Cools et al. (Cools et al., 2002). This task has been associated with DA D2 receptor function (Jocham et al., 2009), which is why we selected it for this study design. On each trial, subjects are presented simultaneously with two abstract visual patterns in the left and right visual fields (location randomized). On each trial, the same two patterns are

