All paper data will be stored in locked cabinets in the PI office space at UC San Diego Health Eating Disorders Center for Treatment and Research ([name]). All electronic data will be stored on the VRD server created for [name] lab by the ACTRI (see section 16 PRIVACY AND CONFIDENTIALITY CONSIDERATIONS INCLUDING DATA ACCESS AND MANAGEMENT below for more details).

We will extract for both tasks mean parameter estimates from 18 predefined anatomical regions of interest (ROIs) (<http://marsbar.sourceforge.net/>), automated anatomical labeling Atlas, AAL (Tzourio-Mazoyer et al., 2002) based on previous studies (DeGuzman et al., 2017): dorsal and ventral anterior insula, caudate head, gyrus rectus, medial, middle and inferior OFC, ventral striatum (O'Doherty et al., 2004) and nucleus accumbens (Breiter et al., 1997). Extracted ROI data will be analyzed using SPSS 24 (IBM statistical software) using repeated measures ANCOVA. Extracted regional brain activation parameter estimates will be tested for normality with the Shapiro-Wilk test, rank-transformed when non-normally distributed and analyzed using repeated measures ANCOVA with covariates as in previous studies to account for confounding factors such as comorbidity or medication (DeGuzman et al., 2017). Spearman's rank will be used for correlation analyses and controlled for multiple comparisons using bootstrapping (1000 samples) (Westfall, 2011). We will also conduct exploratory whole-brain analyses to test for areas of interest outside of our predefined ROIs and create PE response maps, with maps thresholded at voxel level $p < 0.05$, FWE corrected (very stringent), 10 voxel minimum cluster contiguity, as well as voxel level $p < 0.001$ and $p < 0.05$ cluster level corrected (exploratory),

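### In the secondary taste-task pathway, regions are chosen by their fit to the prediction-error curve and then compared with that same curve in the same data, so the comparison overstates model fit and can tilt the choice of learning rate

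*Combined protocol and SAP*

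**What the plan says.** Section 9 has a primary and a secondary analysis pathway for the taste task. The secondary one "includes mathematical models that try to bridge brain function and actual behavior". Under *Use of mathematical models and testing of alternate models*, a temporal-difference prediction-error curve is built from each subject's event history with discount factor 0.99 and two learning rates, 0.2 and 0.7. It is convolved with a haemodynamic response and fitted to the imaging data "in order to generate brain regions that respond according to the model". The next sentence reads: "Time activity curves will then be created in order to compare actual with predicted brain response over time".

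The text then says it cannot be predicted whether women with anorexia nervosa (AN) will have a reduced response "or if a different learning rate will apply and explain altered learning response". It closes: "This will be an empirical task during data analysis". It does not say which rate generates the regions, which sample they come from, or by what criterion the rates are compared.

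Separately, the *Data Storage and Data Analysis Plan* in the same section extracts, for both tasks, "mean parameter estimates from 18 predefined anatomical regions of interest (ROIs") for a repeated measures ANCOVA. Exploratory whole-brain prediction-error maps are thresholded either at voxel-level family-wise p<0.05 with at least 10 voxels, or at voxel p<0.001 with cluster-corrected p<0.05.

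**The concern.** Read in order, the same data and the same curve choose the region and then serve to judge how well the region follows the curve. Selection keeps voxels whose noise happens to point the model's way. A later look at those voxels in the same data sees that noise again and counts it as agreement.

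Two things are at stake. The first is the credibility of the model check: good agreement in such regions says little about whether the model is right. The second is the learning-rate question. If regions are generated with one rate and both rates are then compared inside them, the selecting rate has a head start. The plan gives no other rule for settling that question.

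**Working it through.** The documents give no figure for this step, so there is none to reproduce. The check has four parts.

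**Inputs from the documents (Section 9).** 280 trials (100 CS+, 100 CS-, 80 neutral); 20 omissions among the last 90 CS+; 20 unexpected rewards among the CS-; six time points per trial, with the cue at point 1 and reward at point 3; discount 0.99; learning rates 0.2 and 0.7; groups of 20 (*Statistical Power*). **Assumed:** canonical haemodynamic response, white noise, independent voxels, sampling every 2 s (14 s also run), and selection at one-sided voxel p<0.001 without cluster correction.

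**1. Agreement after selection, pure noise.** In 60 simulated experiments of 3000 voxels and 20 subjects, a region appeared in 59.

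| Where fit is judged | Mean correlation with curve | Share positive |
|---|---|---|
| Selected regions, same data | 0.023 | 100% |
| Selected regions, independent data | 0.0003 | 53% |
| Fixed region set beforehand | 0.0000 | 50% |

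A single run with 14 s sampling gave about 0.057 in the same data. The direction of agreement is forced; its size in noise is small.

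**2. Overstatement when there is a real signal.** In a second simulation (22 women; smooth noise of 6 mm FWHM; 3 mm voxels assumed; p<0.001 and at least 10 voxels), a true effect of 0.5 SD appeared as 0.79 SD in the selected regions, a ratio of 0.79/0.5 = 1.58.

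**3. Tilt between learning rates.** Let the fits to the two curves be standard normal with correlation ρ and equal true fit of zero. Given a fit z for the selecting rate, the other has mean ρz and variance 1-ρ². So

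P(selecting rate fits better) = Φ(z(1-ρ)/√(1-ρ²)) = Φ(z√((1-ρ)/(1+ρ))).

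With z about 3.3 for a voxel just past p<0.001:

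- ρ = 0.97: √(0.03/1.97) = 0.123; Φ(0.41) = 66%
- ρ = 0.984: √(0.016/1.984) = 0.090; Φ(0.30) = 62%
- ρ = 0.99: √(0.01/1.99) = 0.071; Φ(0.23) = 59%

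These are single-voxel values. A region averages several voxels, which sharpens the difference: 3000 × 0.001 = 3 voxels are expected by chance, and Φ(√3 × 0.296) = 70% at ρ = 0.984. In the 20-subject simulation the selecting rate won in 61% of experiments when it was 0.2 and in 72% when it was 0.7. The Monte Carlo error is about √(0.67 × 0.33/59) = 6 points, so the two figures are compatible with a common value. The 22-women simulation gave 61-68%, against 46-53% in a predefined region. The two simulations put the correlation of the curves at 0.97 and 0.98.

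**4. How often noise yields a region under the planned thresholds.** A corrected threshold of 0.05 gives about 5% of pure-noise maps with any region. For two independent maps, 1-0.95² = 9.75%. That is an upper guide, because the maps for the two rates are highly correlated.

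**The case against.** The strongest reply is that no formal test is attached to these curves. Under the primary pathway, time activity curves are there to illustrate activation, and they may be meant the same way here. That limits the harm. But the sentence speaks of comparing actual with predicted response, under a heading on testing alternate models, and leads directly into the open question of whether AN involves a reduced response or whether "if a different learning rate will apply and explain altered learning response". If the purpose is description only, the plan should say so.

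A reader might go further and infer that agreement is guaranteed and the model cannot be contradicted. The documents do not support that, for two reasons. First, agreement is forced only once a region has been selected, and the corrected thresholds would leave about 95% of pure-noise maps with nothing to compare. The simulations selected at an uncorrected or looser threshold. Second, what is forced is a positive average association, not agreement in shape. A region responding only to sweet delivery correlates with the prediction-error curve at 0.78 in one check and 0.88 in another. It could easily be selected, yet the model predicts an error of about -0.8 at omissions and the plotted curve would show no dip. The plot can still expose gross misfit.

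A reader might also infer that the AN-versus-control contrast is biased. This has not been shown. The plan does not say which sample generates the regions. With equal groups of 22 pooled for selection, a null simulation found a significant group difference in 4.9% of selected voxels, the nominal rate.

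Nor do the documents take pilot effect sizes from model-selected regions. The *Statistical Power* example is a caudate estimate, and the ANCOVA uses predefined anatomical regions that include caudate head, ventral striatum and insula. The 0.79 against 0.5 SD illustrates the mechanism; it is not the bias of a planned estimate.

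Finally, the learning-rate tilt assumes that one rate selects the regions in which both are compared. The plan is silent on this.

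**Conclusion.** The concern holds for the secondary time-curve comparison in the taste task. As written, the comparison is circular: given a selected region, a positive average association with the curve is built in and fit is overstated. Such agreement is weak evidence for the temporal-difference model.

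The learning-rate tilt is conditional and modest: about 61-72% against 50% when both rates fit equally and one rate selects. It matters because curves correlated at about 0.97-0.99 leave little information to separate the rates, and no comparison criterion is stated. These sizes rest on the assumed haemodynamic response, noise model and selection threshold.

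The primary pathway and the ANCOVA on the 18 predefined regions are untouched. The corrected map thresholds limit how often a pure-noise region arises. Neither bias in the AN-versus-control contrast nor inflation of the pilot effect sizes has been shown.

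**What to change.** In Section 9, under *Use of mathematical models and testing of alternate models*, state that the time activity curves and the comparison of the 0.2 and 0.7 curves are taken from the 18 predefined anatomical regions already listed in the *Data Storage and Data Analysis Plan*.

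For regions found by the whole-brain map, either generate the region with one subject left out and compare actual with predicted response in that subject, repeating over subjects, or label the curves as descriptive only. Name the criterion by which the two rates will be compared. Separating selection from comparison does not supply one.

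The cost is a few sentences and slightly more scripting, with no new data. The apparent fit will be somewhat lower than under the present text. In the noise simulation, separating the steps brought the mean correlation from 0.023 to 0.0003.

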4. ESTIMATED DURATION OF THE STUDY

3 years enrollment, 2 years data analysis (5 years total)

5. LAY LANGUAGE SUMMARY OR SYNOPSIS (no more than one paragraph)

Anorexia nervosa (AN) is an eating disorder associated with intense fear of weight gain, food refusal, and severe weight loss. AN has the highest mortality rate among the psychiatric disorders; however, little is known about biomarkers, and no medication has been approved for AN. Brain reward pathways have a direct impact on the drive to eat, and a variety of neuroimaging studies have suggested altered reward processing in AN. The neurotransmitter dopamine has a central role in the reward circuitry to drive food approach, and the dynamic interplay between dopamine receptor response and food restriction could have implications for the pathophysiology of AN. In this application, we will develop a study protocol and gather pilot data to identify whether specific dopamine D2 challenge drugs can modulate PE response and reversal learning in AN. In this randomized placebo controlled trial we will apply a dopamine D2 receptor agonist, D2 receptor antagonist and placebo to healthy controls and individuals with AN to test their effects on brain reward processing and reversal learning. We expect that those challenge drugs will lead to opposite brain and behavioral response and directly support the involvement of those receptors in brain function in AN. This research will be important to develop neurotransmitter specific pharmacological treatments for AN.

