6. SPECIFIC AIMS

Aim 1. To establish in AN feasibility and acceptability of a study design to understand the contributions of the selective DA D2 receptor agonist bromocriptine on PE and reversal learning.

Hypothesis 1.a. The DA D2 receptor agonist bromocriptine (1.25mg) will enhance fMRI PE response during a taste-reward PE paradigm in AN in ventral striatum and insula compared to placebo.

Hypothesis 1.b. The DA D2 receptor agonist bromocriptine (1.25mg) will enhance reversal learning and striatum brain response in AN during a monetary reversal learning task compared to placebo during fMRI.

Aim 2. To establish in AN feasibility and acceptability of a study design to understand the contributions of the selective DA D2/D3 receptor antagonist amisulpride on PE and reversal learning.

Hypothesis 1.a. The DA D2 receptor antagonist amisulpride (400mg) will reduce fMRI PE response in the insula and ventral striatum compared to placebo.

Hypothesis 1.b. The DA D2 receptor antagonist amisulpride (400mg) will reduce reversal learning and striatum brain response in AN during a monetary reversal learning task compared to placebo during fMRI.

Aim 3. To gather pilot data how fMRI brain response to the DA D2 receptor agonist bromocriptine or antagonist amisulpride differs between individuals with AN and healthy control women.

Hypothesis 3. We expect we will find an indication that bromocriptine will enhance PE (ventral striatum and insula) and reversal learning (frontal cortex) in AN more compared to the control group, while amisulpride causes the opposite.

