Special Pharmacological Considerations. Bromocriptine is an anti-Parkinson medication available in the US. An investigational new drug (IND) application to the Federal Drug Administration (FDA) has been approved, IND # 141908. Amisulpride is an antipsychotic not freely available in the US; however, it can be purchased via Sanofi France as in previous studies (Admon et al., 2017). We have received an IND from the FDA, which allows for legal import of amisulpride. Both medications have a plasma peak of 3 hours, and fMRI will begin for all sessions at that time point after taking active drug or placebo. The half-lives for amisulpride of 12 hours, and 2-8 hours for bromocriptine are short enough to allow 3 days in between studies to suffice the 5 half-lives

rule for medication elimination from the body (neither medication has active metabolites) (Bergemann et al., 2005; Holt et al., 2010; Schatzberg and Nemeroff, 2013).

Handling of Study Medication

Storage Location: UC San Diego Health Eating Disorders Center for Treatment and Research, [name] (PI Office, [name])

Medications will be stored in a locked cabinet in the research office of the PI. That office is embedded in the UC San Diego Health Eating Disorders Research Program office suite, which is locked. Each study drug will be labeled with the statement “Caution: New Drug—Limited by Federal (or United States) law to investigational use.” (§312.6 Labeling of an investigational new drug.).

A randomization protocol will be developed ahead of the study using Research Randomizer (<https://www.randomizer.org>). The PI will randomize the study days for the three medications. A master file with the randomization of medication per subject will be kept by the study monitor ([name]).

While the tablets look slightly different, subjects will not be told what type of medication they receive on either day. Study participants have been drug naïve to any of the study medications, and we do not expect recognition. It is uncertain what specific effects each medication will have on brain function and there will therefore be no implicit bias.

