Each subject will complete three MRI scan days (Study Visit 1, Study Visit 2, and Study Visit 3). On each day, the subject will consume one of the three medications (amisulpride, bromocriptine or placebo). Each subject will complete a baseline scan (P-fMRI), Amisulpride scan (A-fMRI), and Bromocriptine scan (B-fMRI) spaced 3 days apart (2 to 4 day acceptable range). This randomized study has 6 medication study arms listed below:

On the morning of each study day, the PI or other study staff not running the fMRI scanning procedures will provide the study subjects the medication as per randomization. Other study personnel that will run the fMRI scanning procedures will be kept blinded from the applied medication. This will help reduce bias by the study personnel.

There are no rater applied assessments on the study days so there is no rater bias based on the personnel end. The fMRI data are objective and thus unbiased.

The investigator will not supply the investigational drug to any person not authorized under this part to receive it. (§312.61 Control of the investigational drug.)

Neither study drug is a controlled substance. Nevertheless, the study medication packages with the investigational drugs will be in a securely locked, substantially constructed cabinet, in the PI’s office, which is within an office suite that is locked and accessible only to the research personnel.

Should the subject have a serious adverse reaction that required emergency treatment, the PI would be contacted and the blinding of the medication order would be broken in order to allow adequate treatment of the patient by emergency department staff.

Each subject will be randomized to one of the following groups:

1.

Scan 1: P-fMRI
Scan 2: A-fMRI
Scan 3: B-fMRI

2.

Scan 1: P-fMRI
Scan 2: B-fMRI
Scan 3: A-fMRI

3.

Scan 1: A-fMRI
Scan 2: P-fMRI
Scan 3: B-fMRI

4.

Scan 1: A-fMRI
Scan 2: B-fMRI
Scan 3: P-fMRI

5.

Scan 1: B-fMRI
Scan 2: P-fMRI
Scan 3: A-fMRI

6.

Scan 1: B-fMRI
Scan 2: A-fMRI
Scan 3: P-fMRI

Medication dosage

Amisulpride – Single Dose 400 mg and scan 3 hours post ingestion

Bromocriptine – Single Dose 1.25 mg and scan 3 hours post ingestion

Amisulpride

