The feasibility procedures will also include assessment of side effects from the medication. In case a study participant was to have a serious reaction (such as anaphylaxis) 911 would be called immediately and the person transported to the medical emergency room that is located about 500 yards away on campus. The study personnel are trained in basic life support.

Cardiac conduction abnormalities have been noted in individuals with anorexia nervosa. To ensure patient safety, we will only include patients in our study that are considered medically stable by the Medical Director at UC San Diego Health Eating Disorders Center for Treatment and Research (i.e. normal EKG and lab electrolyte values). If the staff at those facilities does not feel their patient is stable enough to complete the fMRI scan, the study will be postponed until she is stable, or the patient will be withdrawn from the study if timing does not allow the scan to be postponed. Study participants will have their blood pressure and heart rate taken prior to study drug administration as well as at the end of each study day. In case there is a significant drop in blood pressure indicating orthostasis during the study or due to the study medication, we will keep study participants in our research space and provide them with fluids and will recheck the blood pressure until

it has normalized. In case there were ongoing indication of orthostasis we will refer the participant to the local emergency room on campus.

Electrocardiogram. The risk is minimal. Any skin irritation from the electrode placement usually lessens within a few minutes of removing the electrode.

Data and Safety Monitoring Plan

Data will be analyzed as above for brain imaging data. The behavioral data will be analyzed using SPSS statistical software on password protected computers. The PI will perform data analysis with some research assistant support.

Subjects will be continuously monitored during their study participation by asking about how subjects feel and if they have any problems while in the study. However, in case of unexpected effects, the PI will report those to UCSD HRPP.

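### The PI sets the drug order, may hand out the drug and analyses the data, and nothing in the plan masks drug condition from the analyst

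*Combined protocol and SAP*

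**What the plan says.** - **Allocation** (section 9, Handling of Study Medication): "The PI will randomize the study days for the three medications". The study monitor keeps the master file. The drugs are stored in the PI's office, and the tablets are not identical in appearance.
- **Dispensing** (same section): on each study morning, "the PI or other study staff not running the fMRI scanning procedures will provide the study subjects the medication as per randomization". The visit descriptions under Timeline have a research assistant give the drug.
- **Masking** (same section): the women are not told which drug they receive. For staff, "Other study personnel that will run the fMRI scanning procedures will be kept blinded from the applied medication". In a serious reaction the order can be unmasked through the PI.
- **Analysis** (section 15, Data and Safety Monitoring Plan): "The PI will perform data analysis with some research assistant support".
- **Stated reason for seeing no bias** (section 9): "The fMRI data are objective and thus unbiased".
- **Expected direction:** the lay summary in section 5 says "We expect that those challenge drugs will lead to opposite brain and behavioral response". Under Aim 1 in section 6, bromocriptine "will enhance fMRI PE response during a taste-reward PE paradigm in AN in ventral striatum and insula compared to placebo". The Aim 2 hypotheses predict a reduction with amisulpride.

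**The concern.** One person generates the allocation, may hand over distinguishable tablets, holds directional hypotheses and then analyses the data. If that person knows which scan is drug and which is placebo, choices made after acquisition can drift toward the predicted result without any intent. Whether a noisy scan is dropped, or which contrast is put forward, are choices of this kind. At stake are the within-woman drug-placebo comparisons in anorexia nervosa that test the hypotheses under Aims 1 and 2. The pilot estimates are also meant to inform later studies, so any bias would carry forward.

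**Working it through.** The plan gives no figure on this point to reproduce. The check sets the passages side by side and then counts the exposure.

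**1. Who knows the drug at each step**
- Order generated: the PI. The monitor holds the master file, but the text does not say that the PI lacks access or keeps no copy.
- Drug handed over: the PI or other staff who do not run the scans.
- Scan run: staff stated to be masked.
- Images transferred (section 16): identifying health information is removed. Nothing is said about concealing drug condition.
- Data analysed: the PI, helped by research assistants. No masking is stated, and no coding of sessions or delayed release of a key is described.

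**2. What is already fixed, and what is open**
- Fixed: the regions named in the hypotheses, 18 regions of interest, the rule for rank transformation (section 9, Data Storage and Data Analysis Plan) and the SPM12 processing steps (section 9, fMRI Image Analysis Pathway).
- Open, main items: there is no rule for excluding a scan, since motion enters only as regressors. Five reversal-learning contrasts are listed with none primary, and Hypothesis 1.b under each aim names no contrast.
- Open, lesser items: covariates are given by example, and subject-level covariates barely move a within-woman drug contrast. Two learning rates (0.2 and 0.7) are used in the secondary pathway, with neither leading.

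**3. Which gaps need masking**
- Scan exclusion depends mainly on masking, because it is judged scan by scan.
- The contrast, the covariates and the learning rate are prespecification gaps. A dated written lock closes them even if the analyst is not masked. Masking without a lock would not close them.

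**4. Exposure**
- Inputs: 44 planned completers (section 10) and three scans each (section 9).
- All women: 44 × 3 = 132 scans.
- Section 10 does not split the 44 by diagnosis, so the anorexia nervosa share needs an assumption:
  - 20 women, the group size in Statistical Power: 20 × 3 = 60.
  - Equal split: 22 × 3 = 66.
  - All 34 enrolled women with anorexia nervosa complete: 34 × 3 = 102. This would leave 44 − 34 = 10 controls.

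**5. Type of code**
- One shared three-letter code for the three conditions has 3! = 6 possible keys for the whole data set and could be guessed from group results.
- With participant-specific codes, each woman separately has 6 possible orders, matching the six arms in section 9.

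**The case against.** The best defence has four parts.

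- **Custody and code-break.** The monitor holds the master file, and an emergency code-break implies that the order is concealed from someone. Both are real but partial. Custody of a list does not mask the person who created it.
- **Objective data.** Image acquisition is not rated by staff, and much of the pipeline is fixed. That narrows the analyst's freedom but does not reach scan exclusion or the choice of contrast.
- **Pilot purpose.** Aims 1 and 2 are framed as feasibility and acceptability, and Statistical Power says that a main goal is to learn about distributions and standard deviations. This limits the weight of the point. It does not remove it, because directional drug-placebo hypotheses are stated under both aims.
- **Scope of the analysis sentence.** In section 15 it directly follows a sentence on behavioural data. The paragraph opens with brain imaging, so covering both is the likelier reading, but the text is not explicit.

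A reader might also infer more than the documents support:

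- *That only scan staff are masked.* The women are also kept untold.
- *That the documents contradict themselves on who gives the drug.* A research assistant who does not run the scans fits both descriptions. The PI is permitted to dispense, not required to.
- *That "It is uncertain what specific effects each medication will have on brain function and there will therefore be no implicit bias" is a claim about the analyst.* It closes a paragraph about participants.
- *That 132 is a ceiling.* It counts planned completers only. Section 20 allows repeat visits, and women who withdraw may leave partial data.
- *That results will be biased.* Nothing shows this. The documents show only that a protection is absent.

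**Conclusion.** The point holds as a gap in analyst masking, and closing it is a cheap improvement. In the text supplied for review, the PI randomises, may dispense and analyses, and no provision conceals drug condition from the analyst while directional hypotheses are in play. The size of any bias cannot be computed. The exposure is about 132 scans if 44 women complete three each; repeat visits or partial data could raise this. Of these, 60 to 102 are scans of women with anorexia nervosa, under the assumptions shown. These are counts of what is exposed, not an error rate. The conclusion rests on reading the section 15 sentence as covering imaging data. The feasibility purpose confines it to the drug-placebo hypotheses under Aims 1 and 2.

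**What to change.** 1. Have someone outside the analysis generate and hold the sequence list. The study monitor would serve if confirmed not to be an analyst; names are removed, so this cannot be judged from the text. Otherwise use another existing staff member.
2. Have that person code the scans and the session-level task and behavioural logs. Use participant-specific codes that hide drug, date and visit order. Keep them separate from the subject number, whose key the PI and lab manager hold (section 11). Restore visit order at key release so that period and order effects can be checked.
3. Have existing staff who neither run the scans nor analyse the data dispense the drug, as section 9 already permits. State this consistently in Handling of Study Medication and in the visit descriptions.
4. Before any drug contrast is run and before the key is released, lock in writing the scan-exclusion rule, the primary reversal contrast, the covariates and the primary learning rate. This lock is worth making even if the PI cannot be fully masked.
5. Replace the section 9 statement that imaging data carry no bias with a statement of who is masked at which step.

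Leave safety reporting and emergency unblinding as written.

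**Cost:** some relabelling, coordination over who dispenses, and one written document. Sample size, visits and scans do not change. Masking will be incomplete, because diagnosis stays visible and the symptom and blood-pressure reports in section 25 may reveal some allocations. The plan should say so.
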